### 1. Abstract

- a. Provide no more than a one page research abstract briefly stating the problem, the research hypothesis, and the importance of the research.

The overall goal of the study is to counter the effects of increased N-methyl-D-aspartate (NMDA)/glutamate receptors in MeCP2-mutation-positive Rett syndrome (RTT) subjects by use of a placebo-controlled trial of dextromethorphan (DM), an agent known to block the NMDA receptor channels. The drug dose of DM will be 5mg/kg/day as this dose showed optimal results in our previous dose-effect study. We anticipate improved cognition and temperament, and reduced seizure frequency.

RTT is a neurodevelopmental disorder with devastating consequences to both brain and systemic neurons. Despite a prominent 50% reduction in the number of synapses, postmortem brain autoradiographic studies demonstrate a striking and disproportionate increase in the number of glutamate/NMDA (N-methyl-D-aspartate) subtype of receptors in the prefrontal cortex, especially in younger patients. DM blocks NMDA receptor channels, which improve some clinical manifestations of RTT (eg, cognitive and behavioral deficits, seizures) by reducing the excitotoxic damage and preventing the degree of intellectual disability over the long term. Presently, there is no effective therapy or definitive treatment for RTT, other than palliative care, therefore, our overall specific aim in this biologically-based study is to test the efficacy of DM vs placebo in RTT to block the disproportionate numbers of glutamate/NMDA receptors in the brain and alleviate symptoms. This study holds promise for improved quality of life for girls with RTT, by helping to reduce the degree of functional impairment in this population. Moreover, this study would lend itself to a mode of therapy for other epileptic conditions also associated with glutamatergic excitotoxicity.

Measurement of cytokines and glutamate in serum and released from peripheral blood mononuclear cells (PBMC): Much of the experimental work has been conducted on the *Mecp2* null mouse. Although the model has provided great insight into the disease, there are distinct differences between the murine model and the human disease. For example, the human disease in many is caused by several mutations, and not only the absence of *MECP2*. Many mutated forms of *MECP2* display some functionality (Gonzales ML and LaSalle JM, The role of MeCP2 in brain development and neurodevelopmental disorders. Current Psych Reports 2010:12:127-34). Multiple mutations described in children with Rett display varying phenotypes in females. The disease phenotype is severe in the male mouse model, however, in the human disease, males carrying mutated *MECP2* usually are few, not frequently recognized, are extremely ill, and therefore not well studied.

Two studies have been recently published suggesting the involvement of the innate immune response in RTT. In one, hippocampal neurons displayed abnormal dendritic morphology in the presence of conditioned media from cultures of *Mecp2*-null microglia. Glutamate was

Date: April 12, 2013

Principal Investigator: [name]

Application Number: NA\_00064949

identified as the mediator causing the damage [2]. (Maezawa, I. and Jin, L. W. (2010) Rett syndrome microglia damage dendrites and synapses by the elevated release of glutamate. *J Neurosci* 30, 5346-56). In the second study, investigators found that *Mecp2* null mice that received a graft of bone marrow cells from wild-type mice survived longer and displayed significant improvements in respiratory function and motor control. Because the benefits of wild-type microglia were diminished by blocking their phagocytic ability, the importance of phagocytic activity in RTT was suggested [3] (Derecki, N. C., Cronk, J. C., Lu, Z., Xu, E., Abbott, S. B., Guyenet, P. G., Kipnis, J. (2012) Wild-type microglia arrest pathology in a mouse model of Rett syndrome. *Nature* 484, 105-9). To determine the relevance of these findings in human monocytes, we developed a model to study *Mecp2* deficiency by transducing peripheral blood mononuclear cells (PBMC) with lentiviral shRNA against MECP2.

**2. Objectives** (include all primary and secondary objectives)

*Primary outcome:* Improve cognition. Cognitive skills will be measured by neuropsychological tests (Mullen Scales of Early Learning).

*Secondary outcome:* Improvement in behavior will be measured by: a) Vineland Adaptive Behavior Scales (VABS); b) behavior and temperament dysregulation will be measured by the Ghuman-Folstein Screen for Social Interaction (SSI).

[figure not shown]
*Exploratory outcome measures:* a) Seizure frequency will be measured by a seizure diary and interim evaluations by neurologists. As commonly used anticonvulsants are not known to change EEG patterns in RTT patients, those on anticonvulsant medications prescribed by their neurologists will continue on the same medications and doses throughout the study; b) Rett Syndrome Behavior Questionnaire (RSBQ); c) Pediatric Quality of Life Inventory (PedsQL version 4). d) Measure cytokines and glutamate in serum released from peripheral blood mononuclear cells (PBMC) in children with Rett Syndrome and determine whether treating children with dextromethorphan modifies the cytokine and glutamate levels. Studies in [name] laboratory have shown elevated responses in human PBMC made MECP2 deficient with lentiviral shRNA against MECP2. We observed increased expression of glutaminase (GLS) mRNA and increased release of glutamate in MECP2 deficient PBMC compared to controls (fig 1). We also observed increased expression of TNF $\alpha$  and IL-6 mRNA (not shown). These responses were inhibited by drugs that block the NF- $\kappa$ B signaling pathway.

**3. Background** (briefly describe pre-clinical and clinical data, current experience with procedures, drug or device, and any other relevant information to justify the research)

Our investigations in RTT as well as that of others demonstrate elevated brain glutamate and its NMDA receptors in children below 10 yrs of age and in the RTT mouse model prior to 7 weeks of age. Additionally, our preliminary therapeutic trial shows that DM, which blocks NMDA receptors, benefits RTT patients by ameliorating some symptoms and improving quality of life. In stage 2 of RTT (1- 4 years of age) acquired skills are lost, with onset of autistic-like features, stereotyped behaviors, and poor hand use accompanied by diffuse slowing and frontocentral spikes on EEG. Mental retardation (MR) and respiratory irregularities in the wake period become evident in stages 2 and 3 (5-10 yrs). In stage 3, patients appear to recover from the autistic tendencies but all other symptoms remain, with poor weight gain, gastrointestinal problems, vasomotor instability of extremities, and osteopenia, as concomitant findings. Interventions to reduce some aspects of the morbidity and mortality in stages 2 and 3 that could be related to the neuroexcitotoxicity seen in Rett syndrome require early intervention. Neuroexcitotoxic injury, as also shown in cultured neurons to elevated glutamate levels by Russell *et al.* and Maezawa and Jin, needs to be stabilized

to prevent progressive brain injury, thus reducing long term effects of mental retardation and ancillary deficits.

The results in [name] experimental studies of PBMC shown in Fig below warrant evaluation of the effects of DM treatment as compared to those who are on placebo.

**Figure 1. GLS mRNA levels and glutamate release in MeCP2 deficient leukocytes.**

Glutaminase (GLS) mRNA was measured from total RNA isolated from PBMC transduced with either the MECP2 shRNA lentiviral vector or control. GLS mRNA was normalized to GAPDH mRNA (A). Similarly, glutamate released into the media was measured in transduced and control cultures (B). Some cultures were also treated with the NF- $\kappa$ B inhibitors Act and JSH. The data are expressed as a mean of triplicates of a representative experiment  $\pm$  S.E.M. \*  $p<0.05$ , \*\*  $p<0.01$  and \*\*\* $p<0.001$  using ANOVA with Dunnetts multiple comparisons post hoc test.

#### 4. Study Procedures

##### a. Study design, including the sequence and timing of study procedures

(distinguish research procedures from those that are part of routine care).

Sixty subjects with clinical features of RTT, with a known mutation in the *MECP2* gene, will be studied in this placebo controlled trial of DM in RTT. We will use a randomization scheme instituted by personnel not directly involved with the study subjects. The DM group will take 5mg/kg/day orally in 2 divided doses 12 hours apart. The pharmacists will dispense the DM or placebo to both the in- and out-patient study participants. The study population will consist of 30 subjects in the placebo group and 30 subjects in the DM group. We will randomize patients to dextromethorphan or placebo using a computer-generated randomization sequence with varying block sizes that is stratified for age (2-5 years vs. 6-10 years). Given the moderate sample size, using pre-stratification will further increase the probability for having balanced and comparable treatment groups. The statistician will generate the randomization list for the JHH Investigational Drug Service. By always keeping the randomization list separate and inaccessible to study investigators, we will ensure concealment of random allocation.

*Assessment of treatment efficacy:* Subjects will be followed at regular intervals during the study by a series of evaluations, as indicated below. All subjects in the study will be followed until the last recruited subject has completed 3 months of the trial. In light of the large number of RTT patients <10 years of age available for study, we believe we can recruit 60 subjects within the 3-year study period.

All procedures are for research purposes to assess the effectiveness of DM vs. placebo.

Date: April 12, 2013

Principal Investigator: [name]

Application Number: NA\_00064949

Since DM may be slowly excreted in about 10-20% of the normal population, a pharmacokinetics (PK) study will be performed by administering one 2.5mg/kg oral dose of immediate release DM-to be given during the first hospital admission (after the baseline blood sample for PK testing is obtained) to determine the rate of metabolism of DM. Drug levels will be monitored twice by a blood test: a) at peak level (3 hours) and, b) at the lowest level (12 hours). Should a subject be found to be an intermediate or slow metabolizer of DM, she would be excluded from this study because a safe dose of DM could not be determined. The study drug or placebo would not be started until after results from the baseline visit PK testing are available to the study team about the DM's PK status of the participant. Following the PK study, the rapid metabolizers will be included in the 3-month trial, and will take DM at a dose of 5mg/kg/day or an equal volume of placebo, given in two divided doses, exactly 12 hours apart. At the end of the study the code is broken to determine whether DM shows more effectiveness than placebo.

The test procedures/evaluations/assessments per the study protocol will be performed during two 3-day inpatient admissions to the Johns Hopkins Pediatric Clinical Research Unit (PCRU). Subjects will be admitted as follows: 1) the initial admission will be prior to the initiation of the placebo-controlled DM trial, and 2) the second admission will be at the end of 3 months of the study. Any test result done as part of the study protocol that shows a deviation from normal, is to be repeated, as a clinically indicated test. In addition to the baseline and end of study admissions, all subjects will be required to have two interim evaluations at 2 weeks and at 1 month during this study (as noted below) either by us in our outpatient clinic or by their local physician, with no more than a two-week delay being permitted to obtain the required interim tests.

Upon discharge from the initial (baseline) PCRU admission, all study participants will be closely followed by the research associate or research nurse by at least weekly telephone interviews during the first month, and then at least once/month telephone interviews through the end of the 3-month study.

*Study Protocol procedures: (all test results/performances will be compared to subjects' baseline values):*

- 1) We will request parents to provide us with medical records or release of information from appropriate sources; i.e, MeCp2 gene test report, birth and developmental history, and neurological reports.
- 2) a) General physical/neurological examinations; (approximate time allotted is 1 hour);  
b) EKG (due to reports of prolonged QTC interval); (time allotted is ~20 minutes);  
c) Orthostatic blood pressure assessment (due to autonomic dysfunction); (time allotted is ~10 minutes).

These tests will be performed before initiation of DM or placebo during the baseline inpatient admission, and are to be repeated at the required two interim evaluations at 2 weeks and 1 month during the trial, and again during the 3-month end of study admission.

3) Blood tests:

**Initial, baseline admission:** a) Routine CBC with differential (2cc); b) comprehensive metabolic panel (CMP) and liver function tests (LFTs) (3 cc); c) DM pharmacokinetic assay (12cc divided for 3 draws at baseline, peak and lowest level); d) For those already getting blood drawn for CBC, CMP and DM level, we will collect an additional one cc of blood to obtain serum and peripheral blood mononuclear cells in pre treated children. The blood will be immediately transferred to [name] laboratory and processed. Serum and cells will be frozen and assays will be performed when sufficient numbers of samples are collected. Cytokines will be measured by ELISA and cellular responses will be examined by flow cytometry.

Date: April 12, 2013

Principal Investigator: [name]

Application Number: NA\_00064949

- Interim evaluations at 2 weeks and 1 month:** a) Routine CBC with differential (2cc); b) CMP and LFT (3cc); c) DM level (6cc).
- 4) **End of study (3-month) admission:** a) Routine CBC with differential (2cc); b) CMP and LFT (3cc); c) DM level (6cc). d) For those already getting blood drawn for CBC, CMP and DM level, we will collect an additional one cc of blood to obtain serum and peripheral blood mononuclear cells in post treated children. The blood will be immediately transferred to [name] laboratory and processed. Serum and cells will be frozen and assays will be performed when sufficient numbers of samples are collected. Cytokines will be measured by ELISA and cellular responses will be examined by flow cytometry. Approximately 2cc blood for a serum pregnancy test will be obtained on the first day of admission (takes about 5 minutes) in those who are post-menarchal, which will be very few given the younger age of this study population (to be obtained before initiation of DM during the baseline admission and again during the end of study admission after 3 months). Parents will be informed about the need and rationale (ie, drug effect) for the pregnancy test. If they decline the pregnancy test because of any concerns, they will be unable to participate in this study.
  - 5) Neuropsychological testing (approximately 2 - 2 1/2 hours) by a neuropsychologist to assess cognitive status (Mullen Scales of Early Learning (MULLEN), Vineland Adaptive Behavior Scales (VABS), will be performed during the baseline admission and at the 3-month end of study admission.
  - 6) Neurobehavioral evaluation (approximately 1 hour) by a child psychiatrist to assess behavioral abnormalities. Parent will complete behavioral checklists/questionnaires: Ghuman-Folstein Screen for Social Interaction (SSI), Rett Syndrome Behavior Questionnaire (RSBQ) upon baseline admission and at the 3-month end of study admission.
  - 7) Nutritional assessment (approximately 45 minutes) for monitoring growth indices (height, weight, head circumference, body mass index) and nutritional intake. A 3-day food record will be sent to families prior to admission (see Oral Consent form).
  - 8) Quality of Life questionnaire, the Pediatric Quality of Life Inventory (Peds QL version 4) to assess the child's physical, emotional, and social well-being from the perspective of a parent or guardian, to be obtained at the baseline and 3-month end of study admissions.
  - 9) We will assess compliance including drug and/or placebo intake or compliance with the study protocol including the two required interim evaluations by at least weekly telephone intake phone calls by our research nurse or research associate during the first month of the study, and by at least monthly telephone intake phone calls until the end of the 3-month study.
  - 10) After hours pediatric resident coverage in the PCRU will be provided by the Neill team, the hospital's standard procedure.
  - 11) De-identified information will be shared with our research collaborators.
- b. Study duration and number of study visits required of research participants.  
We anticipate to complete the study within 3 years. The test procedures as part of the study protocol will be performed during two 3-day inpatient admissions to the pediatric clinical research unit (PCRU) in the Johns Hopkins Institute for Clinical and Translations Research (ICTR). Subjects will be admitted to the PCRU twice to assess changes in primary, secondary, and exploratory outcome variables. The baseline admission will be prior to initiation of the 3-month study and the second admission will be after 3 months of the trial.

Date: April 12, 2013

Principal Investigator: [name]

Application Number: NA\_00064949

In addition, subjects will have two interim evaluations required at 2 weeks and 1 month during this study to be done either in our outpatient Clinic or by their local physician. The neurological evaluation will take about one half hour, the EKG will take about 20 minutes, and the blood draw will take about 15 minutes.

- c. Blinding, including justification for blinding or not blinding the trial, if applicable.  
The study is a double blind placebo-controlled drug trial to determine the effect of DM (5mg/kg/day) versus placebo.
- d. Justification of why participants will not receive routine care or will have current therapy stopped. N/A
- e. Justification for inclusion of a placebo or non-treatment group.  
The previous dose response study was considered by the FDA to be biased as all participants knew the dose of the medication; therefore, the FDA suggested a placebo controlled trial. Also the previous study has shown no side effects on any of the doses including the highest dose of 5mg/kg/day in 2 divided doses of DM in RTT subjects of similar ages.
- f. Definition of treatment failure or participant removal criteria.  

## 5. Inclusion/Exclusion Criteria

Date: April 12, 2013

Principal Investigator: [name]

Application Number: NA\_00064949

Inclusion criteria: 1) those with classic or atypical RTT who have a proven mutation in the *MECP2* gene; 2) subjects must be between 2 years - 9.99 years of age.

Exclusion criteria: 1) those without an established mutation in the *MECP2* gene; 2) those with mutations in the *MECP2* gene but who have had brain resection or surgical intervention; for example, tumor, hydrocephalus, severe head trauma; or, an associated severe medical illnesses such as vasculopathies, malignancies, diabetes, thyroid dysfunction, etc; 3) those on medications that could interact with DM, e.g. MAO inhibitors, SSRI, sibutramine etc. to avoid a serotonin syndrome; quinidine and drugs metabolized by the CYP450 isoform CYP2D6 (e.g. amiodarone, haloperidol, propfenone, thioridazine); 4) those proven to be intermediate or slow metabolizers of DM; 5) those with reported adverse reactions to DM; 6) those whose pregnancy test is positive; 7) those showing poor compliance with any aspect of the study; 8) foster children.

## 6. **Drugs/ Substances/ Devices**

- a. The rationale for choosing the drug and dose or for choosing the device to be used.  
DM blocks NMDA/glutamate receptors, which are markedly increased in younger RTT patients and are hypothesized to cause excitotoxic epileptic encephalopathy.
- b. Justification and safety information if FDA approved drugs will be administered for non-FDA approved indications or if doses or routes of administration or participant populations are changed.  
Blocking NMDA receptors will prevent neuroexcitotoxic injury to brains, as in non-ketotic hyperglycinemia, where it has been given to neonates in a fairly high dose (5-35mg/kg), which was well-tolerated.
- c. Justification and safety information if non-FDA approved drugs without an IND will be administered. N/A

## 7. **Study Statistics**

- a. Primary outcome variable. Improvement in cognition.
- b. Secondary outcome variables. Improvement in behavior.  
*Exploratory outcome variables:* Reduced seizure frequency; improvement in the Quality of Life and Rett Syndrome Behavior questionnaires.
- c. Statistical plan including sample size justification and interim data analysis.

The data will be analyzed when all 60 participants (30 subjects in the placebo group and 30 subjects in the DM group) have completed the 3-month the trial.

Neuropsychological measures for Mullen and VABS: Subjects will be assigned to intervention in a randomized manner as described in randomization. The neuropsychological measures to establish relative cognitive and adaptive competence of the 2 groups to be comparable, age equivalent scores on the Mullen and VABS measures will be compared between groups using 2x2 repeated measures analysis of variance (ANOVA) with the between subjects factor being drug or placebo and within subjects factor being time. Changes in cognitive measures (Mullen and VABS) will be correlated with the behavior measures and seizure frequency.

We based our sample size on the primary outcome, which are the receptive language age equivalent scores on the Mullen scale. There is no established minimal important difference for the Mullen score that is widely accepted and would provide a reasonable effect estimate for sample size calculation. However, a distribution-based estimate of the minimal important difference can be derived from the standard errors of measurement (SEM) that have been

Date: April 12, 2013

Principal Investigator: [name]

Application Number: NA\_00064949

reported for the Mullen subscales (chapter 6 of the Mullen scale) and 1 SEM provides an accepted approximation of the minimal important difference. To detect a 4 point difference (1 SEM) in the receptive language age equivalent scores on the Mullen scale between the groups and assuming a standard deviation of 5 points (based on our pilot data) we need a total sample size (both groups) of 50 patients at a significance level of 0.05 (two-sided) and a power of 80%. Assuming a dropout rate of around 15% the required sample size increases to 60 patients.

*Sample size calculation.* Measurement of cytokines and glutamate in serum and released from peripheral blood mononuclear cells: We estimate that 12 children in each group (placebo and drug treated) will be needed using an  $\alpha=0.05$  and a  $\text{power}=0.8$ .

We will randomize patients to dextromethorphan or placebo using a computer-generated randomization sequence with varying block sizes that is stratified for age (2-5 years vs. 6-10 years). Given the moderate sample size, using pre-stratification will further increase the probability for having balanced and comparable treatment groups. A Johns Hopkins statistician will generate the randomization lists. By always keeping the randomization list separate and inaccessible for study investigators, we will ensure concealment of random allocation.

d. Early stopping rules. None.

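### The Mullen repeated-measures ANOVA is valid when read as group-by-time, but an ANCOVA on baseline score and age stratum would generally be at least as efficient, at almost no cost

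*Combined protocol and SAP*

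**What the plan says.** Section 7c gives the efficacy analysis in one sentence: "age equivalent scores on the Mullen and VABS measures will be compared between groups using 2x2 repeated measures analysis of variance (ANOVA". That sentence goes on to define the model's two factors: "with the between subjects factor being drug or placebo and within subjects factor being time". It lists no covariate, no stratum and no tested term. The next sentence adds that "Changes in cognitive measures (Mullen and VABS) will be correlated with the behavior measures and seizure frequency".

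The sample size in the same section is a comparison of two means. It is set "To detect a 4 point difference (1 SEM) in the receptive language age equivalent scores on the Mullen scale between the groups", and the text continues: "assuming a standard deviation of 5 points (based on our pilot data) we need a total sample size (both groups) of 50 patients", at two-sided 0.05 and 80% power. About 15% dropout takes 50 to 60. The text does not say whether the SD of 5 belongs to a single score or to change, and it gives no correlation between visits.

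Three other places bear on the analysis:

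- Section 4a, item 5: neuropsychological testing, including the Mullen, "will be performed during the baseline admission and at the 3-month end of study admission".
- Section 4a, heading of the procedures list: "all test results/performances will be compared to subjects' baseline values". Section 4b: the two admissions are "to assess changes in primary, secondary, and exploratory outcome variables".
- Sections 4a and 7c: randomization is stratified by age, 2-5 against 6-10 years.

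**The concern.** With one score before treatment and one after, the group-by-time term of a 2x2 repeated-measures ANOVA is the two-sample t-test on change. It subtracts the whole baseline score from the 3-month score, as though each baseline point carried over as exactly one point three months later. When the visits correlate less than perfectly, that over-corrects and adds the noise of the baseline measurement to the comparison. ANCOVA estimates the slope from the data instead. The planned model also omits the age stratum, although the trial randomizes within it.

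What is at stake is precision on the primary outcome in a trial of 60 children, using data that will be in hand anyway. Because the plan does not name the tested term or say what SD 5 describes, its power statement is also not tied to a specific test.

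**Working it through.** **Inputs from section 7c.** Difference 4, SD 5, two-sided alpha 0.05, power 80%, 50 evaluable (25 per arm), 60 randomized.

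**Assumptions.** The correlation r between baseline and 3-month scores is not in the documents, so a range is shown. Cases A and B take equal SDs at both visits. No stratum effect is assumed.

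**1. The plan's own figure.** n per arm = 2 × [5 × (1.960 + 0.842) / 4]² = 24.5, rounded up to 25, so 50 in total. This reproduces. 50 / 0.85 = 58.8, which rounds up to 59, close to the stated 60. By noncentral t, 25 per arm gives 79% power, and this is the benchmark below.

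**2. Standard deviations, with s the single-score SD.**

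- Group-by-time (change): s√(2(1 − r)), 48 df.
- ANCOVA on baseline and stratum: s√(1 − r²), 46 df.
- Variance ratio, ANCOVA to change: (1 − r²) / (2(1 − r)) = (1 + r)/2. This never exceeds 1, so with equal SDs ANCOVA can lose only through its two degrees of freedom.

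**3. Case A: SD 5 is a single-score SD.** Noncentral-t power, 25 per arm:

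| r | SD of change | Group-by-time | ANCOVA SD | ANCOVA |
|---|---|---|---|---|
| 0.2 | 6.32 | 59% | 4.90 | 81% |
| 0.5 | 5.00 | 79% | 4.33 | 89% |
| 0.7 | 3.87 | 95% | 3.57 | 97% |
| 0.8 | 3.16 | over 99% | 3.00 | over 99% |

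Group-by-time reaches 80% at r of about 0.51.

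**4. Case B: SD 5 is the SD of change.** Group-by-time has 79% at every r. The ANCOVA SD is 5√((1 + r)/2):

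| r | ANCOVA SD | ANCOVA | Group-by-time |
|---|---|---|---|
| 0.5 | 4.33 | 89% | 79% |
| 0.7 | 4.61 | 85% | 79% |
| 0.9 | 4.87 | 81% | 79% |

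**5. Unequal SDs.** Assume a baseline SD of 5 and a 3-month SD of 6. The SD of change is √(25 + 36 − 60r) and the ANCOVA SD is 6√(1 − r²). At r = 0.2, 0.5 and 0.7, ANCOVA has 65%, 76% and 90%, against 51%, 70% and 89%. ANCOVA is still no worse, but it does not always reach 80%.

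**6. Simulation.** 20,000 trials at 25 per arm, with baseline and a balanced stratum that has no effect, put ANCOVA power within 1.5 points of the formula. The formula ignores chance baseline imbalance. In Case A at r = 0.5 the simulated powers were 88.5% for ANCOVA and 79.4% for group-by-time.

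**The case against.** The strongest reply is that this is a preference about efficiency and not an error. Group-by-time is a valid test under randomization. It does not ignore baseline, since it subtracts each child's own baseline score; baseline is simply not a covariate. At high r the gain vanishes: in Case A both tests exceed 99% from r = 0.8, and in Case B at r = 0.9 ANCOVA gains about two points. The documents neither support nor exclude a low r. No benefit from the stratum has been shown, because nothing relates age to score. All of this stands, and it limits the size of the point.

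A reader might go further and infer that the treatment test could be the group main effect. That term averages in the pre-treatment score and so halves a 4-point benefit to 2, with Case A power of 43% at r = 0.2 and 32% at r = 0.7. The documents make that reading unlikely. The primary outcome is improvement in cognition, results are compared with baseline, and the visits are there to assess changes. The tested term should be named, but those low powers should not be attributed to the plan.

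The reply does not remove the narrower point. In every case computed ANCOVA was at least as powerful, it needs no new data, and including a factor used to stratify randomization is ordinary practice.

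**Conclusion.** The point holds as a nearly free improvement. With equal SDs at both visits and no stratum effect, ANCOVA adds about 22 points of power at r = 0.2 and 10 at r = 0.5 if SD 5 is a single-score SD, and almost nothing from r = 0.8. If SD 5 is the SD of change, it adds about 10, 6 and 2 points at r = 0.5, 0.7 and 0.9. The values of r are assumptions, and the stratum's own contribution cannot be computed from the documents.

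A reader might infer that the trial is underpowered or that 50 is the wrong number. The documents do not support either. The figure of 50 reproduces, and if SD 5 is the SD of change, group-by-time has essentially the stated power. If it is a single-score SD, the power of group-by-time depends on a correlation that the plan does not state, which is a gap and not a demonstrated shortfall.

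**What to change.** In section 7c, specify for the primary outcome: *ANCOVA of the 3-month Mullen receptive-language age-equivalent score on treatment, adjusting for the baseline score and the randomization age stratum; the treatment coefficient, two-sided alpha 0.05, is the primary test.*

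The present ANOVA sentence also covers the VABS and the other Mullen scales, so it should not simply be deleted. Either use the same ANCOVA form for them, or keep the ANOVA sentence for them with group-by-time named as the tested term.

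In the sample-size paragraph, say whether SD 5 is for a single score or for change. Make these changes before the code is broken.

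The cost is wording and two degrees of freedom (48 to 46 at 25 per arm), with no new data, visits or patients.

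### Randomisation is stratified by age, but the planned ANOVA has only drug and time, so it may give up a small, nearly free gain in precision

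*Combined protocol and SAP*

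**What the plan says.** Section 7c specifies a "computer-generated randomization sequence with varying block sizes that is stratified for age (2-5 years vs. 6-10 years"). Section 4a describes the same scheme and gives the reason for it: "using pre-stratification will further increase the probability for having balanced and comparable treatment groups". Balance is the only purpose stated.

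For the Mullen and VABS age-equivalent scores, Section 7c plans a 2x2 repeated measures ANOVA "with the between subjects factor being drug or placebo and within subjects factor being time". The list of factors is complete as written. Neither the age stratum nor any other covariate appears there or elsewhere in the document.

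No sentence names the term in that ANOVA that tests efficacy. Three places point to change from baseline. Section 4a says "all test results/performances will be compared to subjects' baseline values". Section 4b schedules the two admissions "to assess changes in primary, secondary, and exploratory outcome variables". Section 7a reads "Primary outcome variable. Improvement in cognition". In a 2x2 design the change contrast between arms is the drug-by-time interaction.

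The sample size in Section 7c is an unadjusted two-group calculation for a 4-point difference, "assuming a standard deviation of 5 points (based on our pilot data"). It gives 50 children, raised to 60 for dropout of about 15%.

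**The concern.** Blocking within age strata makes the arms nearly equal in age mix, so age variation contributes little to the true sampling error of the treatment difference. An analysis that leaves the stratum out still counts that variation in its error term. The estimated standard error is then too large for the design: the test runs somewhat below its nominal 5% level and the confidence interval is wider than it needs to be.

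How far this applies depends on the quantity tested. Drug-by-time is equivalent to a t-test on change, so a fixed difference in score level between younger and older children drops out. Only an effect of age on the 3-month change remains in the error term. The Background (Section 3) makes such an effect plausible: it describes loss of acquired skills at 1-4 years and a different course at 5-10 years. It gives no size for an effect on receptive language over 3 months.

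At stake is a modest amount of power and interval width in a trial that has little of either to spare.

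**Working it through.** **Inputs from Section 7c:** difference 4 points, SD 5, two-sided alpha 0.05, power 80%, 50 completers (25 per arm), 60 randomised, two age strata.

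**Assumptions, because the documents are silent:** the SD of 5 is the total SD of the 3-month change; the strata are equal in size; the strata differ in mean change by d = 0, 1, 2 or 3 points.

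**Step 1: the plan's own figure.** Per arm, n = 2(1.960 + 0.842)² × 5² / 4² = 24.5, rounded up to 25, so 50 in total, as stated. For dropout, 50 / 0.85 = 58.8, so 59 against the stated 60. With the t distribution, SE = 5 × √(2/25) = 1.414, noncentrality = 4 / 1.414 = 2.828, and power on 48 df is 79.1%.

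**Step 2: stratum in the model.** With equal strata, the stratum accounts for d²/4 of the total variance of 25. The residual SD is √(25 − d²/4), the SE is that SD × √(2/25), and the test has 47 df. Equivalent completers are 50 / (1 − d²/100).

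| d (points) | Share of variance | Residual SD | SE | Power, adjusted | Equivalent completers |
|---|---|---|---|---|---|
| 0 | 0% | 5.000 | 1.414 | 79.1% | 50.0 |
| 1 | 1% | 4.975 | 1.407 | 79.5% | 50.5 |
| 2 | 4% | 4.899 | 1.386 | 80.7% | 52.1 |
| 3 | 9% | 4.770 | 1.349 | 82.7% | 54.9 |

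**Step 3: simulation of the design.** There were 40,000 trials per setting: 60 children in permuted blocks of 2, 4 or 6 within two strata, 10 lost at random, and total SD of change held at 5. The Monte Carlo standard error is about 0.1 percentage points for type I error and 0.2 for power. Each cell shows unadjusted vs stratum-adjusted.

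| d (points) | Type I error | Power | Mean 95% CI width |
|---|---|---|---|
| 0 | 5.0% vs 5.0% | 79.2% vs 78.9% | 5.67 vs 5.68 |
| 1 | 4.8% vs 4.9% | 79.3% vs 79.4% | 5.67 vs 5.66 |
| 2 | 4.5% vs 4.8% | 79.1% vs 80.2% | 5.67 vs 5.57 |
| 3 | 4.3% vs 5.0% | 79.5% vs 82.1% | 5.67 vs 5.42 |

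With strata split 30/70, power is 79.0% vs 80.0% at 2 points and 80.0% vs 82.2% at 3 points.

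**Step 4: level differences cancel.** Stratum differences in score level of 0, 5 or 10 points leave the unadjusted drug-by-time test at type I error 4.9-5.0% and power about 79%.

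**Step 5: which term matters.** In a mixed model fitted to one simulated dataset, the drug-by-time SE was 1.428 without the stratum, 1.428 with a stratum main effect only, and 1.383 once stratum-by-time was added.

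**Step 6: baseline as a further covariate (a separate source of gain).** With no age effect on change, power with stratum and baseline in the model is 78.0%, 79.1% and 84.5% for assumed baseline-change correlations of 0, −0.2 and −0.4. Unadjusted power is about 79% throughout.

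**The case against.** The unadjusted analysis is valid and, if anything, conservative. It keeps about 79% power in every setting above, which is what 50 completers deliver under the plan's own assumptions. Stratification was introduced for balance, and balance is achieved without adjustment. A gain of more than one percentage point of power needs a stratum difference in change of 2 to 3 points, which is 50-75% of the 4-point effect the trial is sized for. At 1 point the gain is within simulation error, and at 0 there is none. The size also rests on two readings that the plan does not state: that drug-by-time is the efficacy test, and that the SD of 5 is an SD of change. The baseline-covariate figures concern a different question from the stratum.

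All of this stands as a limit on the size. The loss is conditional, and the 84.5% figure should not be counted as a benefit of stratum adjustment. It does not remove the mismatch: the plan randomises within age groups and then analyses as if it had not. The correction needs only data already collected and costs next to nothing if age proves irrelevant.

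**Conclusion.** The point holds. The analysis in Section 7c omits the factor by which the trial randomises. The consequence is limited to precision: the treatment estimate is not biased, type I error is not inflated and the sample size need not change.

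On the change-from-baseline reading, with an SD of change of 5 and 50 completers, adjustment gains nothing if age does not affect change. By simulation it gains 1.1 percentage points of power at an assumed 2-point stratum difference (79.1% to 80.2%) and 2.6 at 3 points (79.5% to 82.1%). At 3 points the mean interval narrows from 5.67 to 5.42. The omission itself is certain from the text; the size depends on an age effect that the documents do not quantify. It is a recommended improvement rather than a flaw that threatens the trial.

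**What to change.** In Section 7c, name the primary analysis as a linear model for the 3-month Mullen receptive language age-equivalent score adjusted for its baseline value (or for the 3-month change), with treatment and the age stratum used at randomisation as terms. Report the stratum-adjusted difference between arms with its 95% CI as the primary result. If the repeated measures form is kept, include both stratum and stratum-by-time and state that drug-by-time is the efficacy test. Settle this before unblinding, so that no choice between adjusted and unadjusted results remains.

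The cost is one or two sentences, with no new data and no change in N. The stratum uses one degree of freedom. If age has no effect on change, that costs under 0.1 percentage points of power by calculation (79.15% to 79.11%) and about 0.3 in the simulation (79.2% vs 78.9%). Adding baseline uses one more; if neither age nor baseline is related to change, the total cost is about 1.2 points (79.2% vs 78.0%).
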